11.2 VISIT 2A – PRE-ABLATION

The following data must be collected prior to the study procedure:

- Quality of Life questionnaires: VAS pain score, EORTC QLQ-C30 and EORTC QLQ-HCC18;
- Any update to medical/ surgical history;
- Any update to concomitant medications;

- Laboratory tests:
 - Prothrombin Induced by Vitamin K Absence or Antagonist-II (PIVKA-II);
 - Coagulation test (PT, APTT, and INR);
 - Liver function test (AST, ALT, GGT, albumin, indirect, direct and total bilirubin, total protein);
 - Renal function test (BUN, Creatinine and electrolytes (sodium, potassium, and chloride));
 - Complete Blood Count (CBC) (differential cell count and platelet count);
- Evaluation of ECOG Performance Status and ASA score;
- Confirm inclusion and exclusion criteria;
- Date and time of hospital admission.

11.3 VISIT 2B- ABLATION

Data collected during procedure:

- Tumor details (size, type, location) and BCLC Staging (intra-procedure staging);
- Procedure details (ultrasound-guided):
 - Duration of procedure (first probe placement to last probe removal);
 - Duration of ablation;
 - Procedure performed;
 - Anatomical location of ablation;
 - Number of ultrasound scans performed for needle and margin assessment;
 - Number of needle placement attempts per needle;
 - Number of ablations;
 - Ablation settings (power and time);

Some of the above ablation procedure details will be provided to the site via a report generated from NeuWave Medical's Call Home Database. The study site will review the report and enter the procedure details into the clinical database, as applicable.

- Device accountability: Type(s) and no. of probes used;
- MRI and CT scans of the liver (up to 4 days after completion of procedure to confirm complete tumor ablation);
- All Adverse Events and SAEs (if applicable);
- Any update to concomitant medications.

11.4 VISIT 2C- POST-ABLATION

Data collected after the procedure up to discharge from the hospital:

- Quality of Life questionnaire: VAS pain score (at discharge)
- Laboratory tests:
 - Alpha-fetoprotein (AFP) test;
 - Prothrombin Induced by Vitamin K Absence or Antagonist-II (PIVKA-II);
 - Coagulation test (PT, APTT, and INR);
 - Liver function test (AST, ALT, GGT, albumin, indirect, direct and total bilirubin, total protein);
 - Renal function test (BUN, Creatinine and electrolytes (sodium, potassium, and chloride));
 - Complete Blood Count (CBC) (differential cell count and platelet count);
- Date and time of hospital discharge
- All Adverse Events and SAEs (if applicable)

- Any update to concomitant medications and procedures

11.5 VISIT 3 (1 MONTH AFTER ABLATION)

The following data will be collected during this follow-up visit:

- Quality of Life questionnaires: VAS pain score, EORTC QLQ-C30 and EORTC QLQ-HCC18;
- Evaluation of ECOG Performance Status;
- MRI and CT scans of the liver (within 14 days prior to the visit):
 - Complete tumor ablation evaluation, including LTP;
 - Indication for repeat ablation (if applicable);
- Laboratory tests (within 14 days prior to the visit):
 - Alpha-fetoprotein (AFP) test;
 - Prothrombin Induced by Vitamin K Absence or Antagonist-II (PIVKA-II);
 - Coagulation test (PT, APTT, and INR);
 - Liver function test (AST, ALT, GGT, albumin, indirect, direct and total bilirubin, total protein);
 - Renal function test (BUN, Creatinine and electrolytes (sodium, potassium, and chloride));
 - Complete Blood Count (CBC) (differential cell count and platelet count);
- Follow-up post-ablation treatment (if applicable);
- All Adverse Events and SAEs (if applicable);
- Any update to concomitant medications and procedures.

11.6 VISIT 4 (3 MONTHS AFTER ABLATION)

The following data will be collected during this follow-up visit:

- Quality of Life questionnaires: VAS pain score, EORTC QLQ-C30 and EORTC QLQ-HCC18;
- Evaluation of ECOG Performance Status;
- CT scan of the liver (within 14 days prior to the visit):
 - LTP evaluation;
 - Indication for repeat ablation (if applicable);
- Laboratory tests (within 14 days prior to the visit):
 - Alpha-fetoprotein (AFP) test;
 - Prothrombin Induced by Vitamin K Absence or Antagonist-II (PIVKA-II);
 - Coagulation test (PT, APTT, and INR);
 - Liver function test (AST, ALT, GGT, albumin, indirect, direct and total bilirubin, total protein);
 - Renal function test (BUN, Creatinine and electrolytes (sodium, potassium, and chloride));
 - Complete Blood Count (CBC) (differential cell count and platelet count);
- MRI of the liver (once per year of follow-up if applicable, depending on each subject's condition and based on the clinical judgement of the Investigator)
 - LTP evaluation;
 - Indication for repeat ablation (if applicable);
- Follow-up post-ablation treatment (if applicable);
- All Adverse Events and SAEs (if applicable);
- Any update to concomitant medications and procedures.

11.7 VISITS 5 TO 10- FOLLOW-UP (6 MONTHS, 9 MONTHS, 1 YEAR, 18 MONTHS, 2 YEARS, AND 30 MONTHS AFTER ABLATION)

The following data will be collected during each follow-up visit:

- Quality of Life questionnaires: VAS pain score, EORTC QLQ-C30 and EORTC QLQ-HCC18;
- Evaluation of ECOG Performance Status;
- CT Scan of the liver (within 14 days prior to the visit)
 - LTP evaluation;
 - Indication for repeat ablation (if applicable);
- Laboratory tests (within 14 days prior to the visit):
 - Alpha-fetoprotein (AFP) test;
 - Prothrombin Induced by Vitamin K Absence or Antagonist-II (PIVKA-II);
 - Coagulation test (PT, APTT, and INR);
 - Liver function test (AST, ALT, GGT, albumin, indirect, direct and total bilirubin, total protein);
 - Renal function test (BUN, Creatinine and electrolytes (sodium, potassium, and chloride));
 - Complete Blood Count (CBC) (differential cell count and platelet count);
- MRI of the liver (once per year of follow-up if applicable, depending on each subject's condition and based on the clinical judgement of the Investigator):
 - LTP evaluation;
 - Indication for repeat ablation (if applicable);
- Follow-up post-ablation treatment (if applicable);
- Subjects will be evaluated for all adverse events according to the Investigator's standard of care practice during each follow-up visit. Note that for this study, after Visit 4 (3 months), only expected or unexpected serious adverse device effects, life-threatening events, events that result in death and all SAEs with definite, possible, probable or unknown relationship to the study device or study procedure will be reported to the Sponsor, if applicable;
- Any update to concomitant medications and procedures.

11.8 VISIT 11- END OF STUDY VISIT (3 YEARS AFTER ABLATION)

The following data will be collected during the final follow-up visit:

- Quality of Life questionnaires: VAS pain score, EORTC QLQ-C30 and EORTC QLQ-HCC18;
- Evaluation of ECOG Performance Status;
- CT Scan of the liver (within 14 days prior to the visit)
 - LTP evaluation;
 - Indication for repeat ablation (if applicable);
- Laboratory tests (within 14 days prior to the visit):
 - Alpha-fetoprotein (AFP) test;
 - Prothrombin Induced by Vitamin K Absence or Antagonist-II (PIVKA-II);
 - Coagulation test (PT, APTT, and INR);
 - Liver function test (AST, ALT, GGT, albumin, indirect, direct and total bilirubin, total protein);
 - Renal function test (BUN, Creatinine and electrolytes (sodium, potassium, and chloride));
 - Complete Blood Count (CBC) (differential cell count and platelet count);

- MRI of the liver (once per year of follow-up if applicable, depending on each subject's condition and based on the clinical judgement of the Investigator)
 - LTP evaluation;
 - Indication for repeat ablation (if applicable);
- Follow-up post-ablation treatment (if applicable);
- Subjects will be evaluated for all adverse events according to the Investigator's standard of care practice during each follow-up visit. Note that for this study, after Visit 4 (3 months), only expected or unexpected serious adverse device effects, life-threatening events, events that result in death and all SAEs with definite, possible, probable or unknown relationship to the study device or study procedure will be reported to the Sponsor, if applicable;
- Any update to concomitant medications and procedures;
- Date of study completion.

11.9 UNSCHEDULED VISIT

Unscheduled visits are for those that are procedure, device, or disease related.

The following data will be collected during each unscheduled visit:

- Reason for the unscheduled visit;
- Follow-up post-ablation treatment (if applicable);
- Adverse Events (if applicable). Subjects will be evaluated for all adverse events according to the Investigator's standard of care practice during each follow-up visit. Note that for this study, from study treatment to Visit 4 (3 months), all AEs and SAEs will be reported to the Sponsor, and after Visit 4 (3 months), only expected or unexpected serious adverse device effects, life-threatening events, events that result in death and all SAEs with definite, possible, probable or unknown relationship to the study device or study procedure will be reported to the Sponsor, if applicable;
- Any update to concomitant medications and procedures.

11.10 REDUCED FOLLOW-UP VISIT

This visit can be a clinic visit or a phone contact visit which will occur every 6 months (+/-28 days) from the day of the first ablation. The following data will be collected only for subjects who have progressed or recurred following the first ablation and are retreated with any treatment post progression:

- Follow-up post-ablation treatment (if applicable);
- Any additional progression(s)/ recurrence(s);
- Survival status;
- Adverse Events (if applicable). Subjects will be evaluated for all adverse events according to the Investigator's standard of care practice during each follow-up visit. Note that for this study, after Visit 4 (3 months), only expected or unexpected serious adverse device effects, life-threatening events, events that result in death and all SAEs with definite, possible, probable or unknown relationship to the study device or study procedure will be reported to the Sponsor, if applicable;
- QOL questionnaires

For subjects on the Reduced Follow-up schedule 6 monthly visits occur until approximately 3 years post ablation.

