Inclusion/Exclusion Criteria	X													
VAS Pain Score	X			X	X	X	X	X	X	X	X	X	X	
EORTC QLQ-C30	X			X	X	X	X	X	X	X	X	X	X	
EORTC QLQ-HCC18	X			X	X	X	X	X	X	X	X	X	X	
CT Scan (Liver)	X		X	X	X	X	X	X	X	X	X	X	X	
MRI (Liver) ⁹	X		X	X	X	X	X	X	X	X	X	X	X	
Ultrasound (Liver) ⁹	X		X	X	X	X	X	X	X	X	X	X	X	
Coagulation Test ¹¹	X		X	X	X	X	X	X	X	X	X	X	X	
Liver Function Test ¹²	X		X	X	X	X	X	X	X	X	X	X	X	
Renal Function Test ¹³	X		X	X	X	X	X	X	X	X	X	X	X	
Complete blood count (CBC) ¹⁴	X		X	X	X	X	X	X	X	X	X	X	X	
Alpha-fetoprotein (AFP) ¹⁵	X		X	X	X	X	X	X	X	X	X	X	X	
PIVKA-II ¹⁶	X		X	X	X	X	X	X	X	X	X	X	X	
Pregnancy Test ¹⁷	X		X	X	X	X	X	X	X	X	X	X	X	
Tumor Size, Type and Location	X		X	X	X	X	X	X	X	X	X	X	X	
BCLC Staging	X		X	X	X	X	X	X	X	X	X	X	X	
ECOG Performance Status	X		X	X	X	X	X	X	X	X	X	X	X	
Child-Pugh Score	X		X	X	X	X	X	X	X	X	X	X	X	
ASA Score	X		X	X	X	X	X	X	X	X	X	X	X	
Procedure Details ⁶			X											
Device Accountability			X											

Visit No. Visit	Visit1: Screening	Visit2A Pre-Ablation	Visit2B Ablation	Visit2C Post-Ablation	Visit3 1 month	Visit4 3 months	Visit5 6 months	Visit6 9 months	Visit7 1 year	Visit8 18 months	Visit9 2 years	Visit10 30 months	Visit11 3 years	USV Unscheduled Visit ⁸
Interval Windows	Within 5 weeks before ablation	-2 to 0 days	Day 0= Ablation of index tumor	0 to 4 days	1 month (+/- 14 days) after ablation	3 months (+/-28days) after ablation	6 months (+/-28 days) after ablation	9 months (+/-28 days) after ablation	12 months (+/-28 days) after ablation	18 months (+/-28 days) after ablation	24 months (+/-28 days) after ablation	30 months (+/-56 days) after ablation	36 months (+/-28 days) after ablation	NA
Study Activity														
Length of Hospital Stay		X		X										
Complete Tumor Ablation Evaluation			X		X									
LTP Evaluation					X	X	X	X	X	X	X	X	X	
Follow-up Post-ablation Treatment ⁷					X	X	X	X	X	X	X	X	X	X
Concomitant Medications	X	X	X	X	X	X	X	X	X	X	X	X	X	X
Relevant Concomitant Procedures				X	X	X	X	X	X	X	X	X	X	X
Adverse Event and SAEs ⁶			X	X	X	X	X	X	X	X	X	X	X	X

Notes:

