8. Adverse Event and SAEs: Subjects will be assessed for safety from day of ablation through the 3-year follow-up. All AEs and SAEs will be reported from the day of the ablation up to 3 months after the ablation procedure. Expected serious adverse device effects (SADE), unexpected serious adverse device effects (USADE), life-threatening events, or events that result in death, and all SAEs with definite, possible, probable or unknown relationship to the study device or study procedure, will be reported from day of the ablation through the 3-year follow-up.
9. Unscheduled visits are only for those which are procedure, device or disease related.

NOTE:

- Subjects who have recurred at the target lesion or progressed with a new lesion following the first ablation, and are treated with any treatment post progression will be followed every 6 months (+/-28 days) from the day of the first ablation as a clinic visit or, if clinic visit is not possible, a phone contact visit (if a clinic visit is not possible). This will be called a "Reduced Follow-Up Schedule."

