7.2 STUDY ENDPOINTS

Primary:

Technical Success, defined as complete tumor ablation with adequate or insufficient margin, based on contrast-enhanced MRI and CT scans immediately following the ablation procedure.

Secondary:

- Primary Technique Efficacy, defined as complete tumor ablation with adequate or insufficient ablation margin, based on contrast-enhanced MRI and CT scans follow-up at 1 month after the ablation procedure;
- Local tumor progression (LTP) rate, evaluated at 1, 3, 6, 9, 12, 18, 24, 30 and 36 months after the ablation of the index tumor;
- Primary efficacy rate, defined as the percentage of target tumors successfully eradicated following the ablation procedure;
- Secondary efficacy rate, defined as the percentage of tumors that have undergone successful repeat ablation following identification of local tumor progression;
- Progression free survival and overall survival rates at 36 months after the ablation procedure;
- Rate of adverse events reported through 3 months and cumulatively through study completion; Quality of Life, as measured by VAS pain score, EORTC QLQ-C30 and EORTC QLQ-HCC18, before the ablation procedure and at each post-ablation visit;
- Health economics associated with the ablation procedure: complete procedure time, ablation time, no. of ablations, length of stay, no. and types of probes used.

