11.11 INDEPENDENT REVIEWER (IR)

An Independent Reviewer, from the site in Korea, will be utilized in this clinical trial in order to

reduce the variability between investigators in assessing the CT images (and as needed, MRI and Ultrasound) and to minimize potential bias. The Independent Reviewer will review all CT scans taken throughout the study (including at screening) using the images stored in the hospital's database and without referring to the radiology imaging report in order to avoid influence in the assessment. All images will be taken in accordance with the hospital's Standard of Care. At baseline, the independent reviewer will confirm the presence of one lesion, and its location, size, and BCLC stage.

According to the standard practice at the site in Korea, the independent review will classify the ablation as:

- complete tumor ablation with adequate margin
- complete tumor ablation with insufficient margin
- incomplete tumor ablation.

This assessment will be done for the scans taken following the ablation procedure (Visit 2, for technical success) and at the 1-month visit (Visit 3, for technical efficacy).

At all post-ablation follow up visits, the central reviewer will assess recurrence of the target lesion, progression, meaning a new lesion(s), or lack thereof. If there is a progression or recurrence, the central reviewer will again assess number of lesions, location, size and BCLC stage.

The assessment by the independent reviewer will only be used for the purpose of statistical analysis while the assessment by the investigators will be used for the treatment of the subjects in the study as well as reported in the analysis.

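### Section 15.8.3 names Kaplan-Meier but admits only subjects observed at each time point, which is not Kaplan-Meier; separately, no read is assigned to repeat-ablation success

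*Combined protocol and SAP*

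**What the plan says.** **Estimator.** Section 15.8.3 gives LTP rates at nine time points from 1 to 36 months by Kaplan-Meier with 95% confidence intervals. The next sentence limits the analysis to subjects who contribute an observation at the time point concerned. A similar summary is then promised for 36-month overall survival (OS) and progression-free survival (PFS). Section 15.8.5 adds that only observed data are summarized, without imputation. Neither section states a censoring rule. The synopsis names Kaplan-Meier for the same LTP rates without the restriction.

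**Reduced follow-up.** Under the notes to Table 1, subjects who recur at the target lesion or progress with a new lesion and "are treated with any treatment post progression will be followed every 6 months (+/-28 days) from the day of the first ablation" are seen in clinic or, "if clinic visit is not possible, a phone contact visit". Section 11.10 says: "This visit can be a clinic visit or a phone contact visit which will occur every 6 months". Its data list covers post-ablation treatment, further progression or recurrence, survival status, adverse events and quality of life. It has no CT, MRI or LTP evaluation. The unscheduled-visit list (11.9) has no imaging either.

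**Read of ablation success.** The secondary efficacy rate (7.2) is "the percentage of tumors that have undergone successful repeat ablation following identification of local tumor progression". In Table 1 the row "Complete Tumor Ablation Evaluation" is marked only at Visits 2B and 3. Section 11.11 says of the three-class read: "This assessment will be done for the scans taken following the ablation procedure (Visit 2, for technical success) and at the 1-month visit". The same section has the independent reviewer read every CT taken, and adds: "At all post-ablation follow up visits, the central reviewer will assess recurrence of the target lesion".

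**The concern.** A Kaplan-Meier estimate at 36 months keeps everyone whose event came earlier, and uses each censored subject for as long as that subject was followed. The restriction in 15.8.3 removes one or both groups, depending on how it is applied. An analyst could count only subjects with a scan in the 36-month window. Another could keep earlier events but drop event-free subjects who left early. The two choices can give very different LTP rates from the same data. Section 15.7 justifies the sample size partly by comparison with published microwave results, so the LTP rate should be defined without ambiguity.

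The reduced schedule adds to this, because a treated recurrence or new lesion moves the subject to a schedule that lists no scans. It also leaves the secondary efficacy rate without an assigned scan, time point or read, although each repeat ablation needs a success call.

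**Working it through.** The plan states no figure that could be reproduced here: the sample size of 30 has no formula, and no precision target is given. Two illustrations show the size.

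**1. The observed-only rule against Kaplan-Meier**

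Inputs from Section 4.2, used as illustrative 36-month LTP rates: 8.2% (HCC series with this device) and 22% (series of larger HCC). Follow-up in those series differs from 36 months. Assumed, because the documents give no values: 30% or 60% with a retreated new lesion by 36 months; 10% or 30% dropout or death by 36 months; independent exponential times; LTP read at the scheduled visits; no scan after the switch. There were 400,000 simulated subjects per scenario. Kaplan-Meier censors at the last scan.

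| True LTP | Kaplan-Meier | A: only subjects scanned at 36 months | B: earlier events kept, early-censored subjects dropped |
|---|---|---|---|
| 8.2% | 8.2-8.3% | 1.4-1.5% | 9.8-14.0% |
| 22% | 22.1% | 4.0-4.1% | 25.8-34.3% |

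Reading A can be checked by hand. With no scans after the switch, the only LTP it can see is LTP arising between the 30- and 36-month visits in subjects free of it until then: 1 - (1 - p)^(6/36).
- p = 0.082: 1 - 0.918^(1/6) = 0.014.
- p = 0.22: 1 - 0.78^(1/6) = 0.041.

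Reading B overstates because its denominator loses event-free subjects. At p = 0.082, 30% new lesions and 10% dropout, the event-free subjects still scanned at 36 months are 0.90 x 0.918 x 0.70^(30/36) = 0.614 of the cohort. A result of 9.8% then means observed events of 0.614 x 0.098/0.902 = 0.067, and 0.067/(0.067 + 0.614) = 0.098.

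The size depends on the no-scan assumption. If half, or all, of the subjects still in the study on reduced follow-up happen to be scanned near month 36:
- True 8.2%: A gives 4.4-4.8% or 5.7-7.0%; B gives 8.1-9.5% or 6.0-8.2%.
- True 22%: A gives 12.3-13.5% or 15.4-19.2%; B gives 21.2-24.6% or 16.2-22.0%.

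These runs do not count index LTP arising after the switch, so part of any shortfall comes from that and not from the rule.

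For OS no simulation is needed. A subject who died before month 36 has no observation at month 36, so the literal rule could exclude the deaths.

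**2. Secondary efficacy rate and index-site LTP after the switch**

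- HCC local progression after microwave ablation in Tables 3 and 4 runs from 3.9% to 25%: 30 x 0.039 = 1.2 and 30 x 0.25 = 7.5, so about 1 to 8 cases. One further HCC series in 4.2, described there as relatively high, gives 39.8% at 1 year: 30 x 0.398 = 11.9. The number re-ablated may be smaller, since other treatments also count.
- Each unread repeat ablation widens the possible range of the rate by 1/2 = 50 points with two cases, or 1/8 = 12.5 points with eight. If the denominator is all 30 tumors, it is 1/30 = 3.3 points.
- Complete data are imprecise too. The exact 95% interval is 15.8-100% for 2/2 (lower limit 0.025^(1/2) = 0.158) and 47.3-99.7% for 7/8.
- Assume 20%, 40% or 60% have a new lesion by 36 months, all retreated and independent of LTP, with literature LTP rates of 3.9%, 8.2% or 25% taken as 36-month rates. A simulation of 4,000,000 subjects per scenario then puts about 9%, 18-19% or 29-31% of index LTP after the switch. That is 0.1 to 2.2 of 30 subjects.

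**The case against.** The observed-only sentence may be loose drafting for the number at risk. Its absurd result for OS suggests so, and Section 15.1 defers detail to a later SAP. That is plausible, but no censoring rule in the documents says so, and the sentence as it stands instructs the analyst otherwise.

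On imaging, the opposing case is stronger. The reviewer already reads every CT taken and assesses target-lesion recurrence at follow-up visits. Section 11.10 already records further progression, Section 11.11 has the investigators' assessments reported too, and the synopsis promises a count, percentage and exact interval for the secondary efficacy rate. A reader might infer that LTP and repeat-ablation data are absent after the switch. The documents do not support that: the data are unscheduled, not missing by design. A reader might also take it as stated that these subjects leave the scheduled CT visits. That is implied by the name and content of the reduced schedule, but nowhere said.

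The figure of 0.1 to 2.2 subjects is therefore an upper bound on index LTP at risk of being missed, since any such subject who has a CT is read. If censoring at the switch is unrelated to LTP risk, it does not by itself bias Kaplan-Meier.

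**Conclusion.** The main point stands as an internal contradiction. Section 15.8.3 names an estimator and then a rule that is incompatible with it, and carries both over to 36-month OS and PFS. Under the stated assumptions, with no scans after the switch, a true LTP of 8.2% could be reported as about 1.4% or 10-14%, and 22% as about 4% or 26-34%. The contradiction follows from the text alone. The sizes are illustrative, and they shrink, with the direction of Reading B uncertain, as more standard-of-care scans are available.

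The imaging point is a cheap improvement to a descriptive endpoint that is imprecise even with full data. It does not reach the primary endpoint, which is read at Visit 2, or Primary Technique Efficacy, read at Visit 3. Nor does the imaging gap undermine PFS or OS: the progression that triggers the switch has already been found, and survival status continues to be recorded. Those two are exposed only through the sentence in 15.8.3.

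A reader might also see a serious conflict between the withdrawal rule in 8.5 for chemotherapy or radiation within 30 days after the procedure and the reduced follow-up of subjects given any post-progression treatment. The overlap is probably small and cannot be sized from the documents; at most, the passages should be reconciled.

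**What to change.** **Section 15.8.3 (and the SAP).** Delete the observed-at-time-point sentence for LTP, PFS and OS. State instead that all Full Analysis Set subjects are included and that earlier events remain events. Subjects without an event are censored at the last index-site scan (LTP), the last disease assessment (PFS) or the last date known alive (OS). Report numbers at risk at each time point. This costs only wording.

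**Sections 11.10 and 11.11.** Record the dates of existing standard-of-care liver scans up to 36 months, including on reduced follow-up. Have the existing reviewer classify each repeat ablation on the existing three-class scale from the first scan after it. Report that scan's timing and modality, because a late scan may mix incomplete ablation with later recurrence. Report how many repeat ablations have no scan. The cost is amendment wording, one eCRF page and a few extra reads. No visit, scan or treatment is added, so timing will be irregular and no scan is guaranteed.

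**Section 8.5.** Reconcile it with the reduced follow-up text on whether outcome follow-up continues for the subjects concerned.
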